2.2.1 Surgical treatment

Radical cervical cancer surgery is the main procedure for the treatment of early-stage cervical cancer and is mainly applicable to cervical cancer above stage IA1 (including IA1 with LVSI, IA2, IB1, IB2, IIA1; and IB3 and IIA2). Compared with standard total hysterectomy, radical hysterectomy for cervical cancer has higher surgical difficulty and corresponding complications because of the larger surgical scope. Abdominal radical hysterectomy for cervical cancer has a history of more than 120 years, and the surgical approach has become very mature, while minimally invasive radical hysterectomy for cervical cancer has also become increasingly mature after nearly 20 years of development. Compared with traditional Abdominal Radical Hysterectomy (ARH), minimally invasive radical hysterectomy has unique advantages, such as less abdominal wall trauma, less pain, clearer vision and less bleeding, less interference with the intestine, and lower postoperative infection rate. Therefore, the 2014 NCCN guideline recommends laparoscopic radical hysterectomy (LRH) to perform radical cervical cancer surgery. Modern standard surgery includes laparoscopic surgery (divided into conventional laparoscopic surgery and robotic-assisted laparoscopic surgery, or multiport laparoscopic surgery and single-port laparoscopic surgery), open surgery, and transvaginal surgery. Because these three procedures are performed on different routes with the same extent of resection, it is intuitively assumed that the results of these three procedures are the same, and therefore most previous studies have focused on operative time, intraoperative bleeding, length of hospital stay, and cost, rather than survival indicators such as progression free survival (PFS) and overall Survival (OS). Only a few previous small

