studies have evaluated the survival benefit of Laparoscopic Radical Hysterectomy (LRH) for cervical cancer: in terms of PFS [5-10], LRH was not inferior to ARH, while laparoscopy was superior to open surgery in terms of operative time, intraoperative bleeding, and length of hospital stay. In November of 2018, the New England Journal of Medicine published two research reports comparing abdominal and minimally invasive radical cervical cancer surgery in the same period, which have shocked the entire gynecology field. The retrospective cohort study concluded [11] that over a median follow-up of 45 months, the 4-year mortality rate was 9.1% for women who underwent minimally invasive surgery and 5.3% for women who underwent open surgery (hazard ratio 1.65; 95% confidence interval 1.22-2.22); prior to the use of minimally invasive radical hysterectomy (i.e., from 2000 to 2006), the 4-year overall survival rate for women undergoing radical hysterectomy remained stable; while the overall survival rate decreased by 0.8% (95% CI, 0.3-1.4) per year after 2006 with the application of minimally invasive surgery,. Another study published in the New England Journal of Medicine in late 2018 (the Laparoscopic Approach to Cervical Cancer, LACC trial) was a Randomized Clinical Trial (RCT), which showed that the 4.5-year PFS rate was 86.0% in the minimally invasive surgery group and 96.5% in the open surgery group, with a difference of -10.6 percentage points (95% CI -16.4 to -4.7); minimally invasive surgery was associated with lower disease-free survival (PFS) compared with open surgery [(3-year PFS was 91.2% vs. 97.1%; hazard ratio for relapse or death of cervical cancer was 3.74; 95% CI (1.63 to 8.58)] [12]. Both studies suggest that minimally invasive radical cervical surgery is associated with lower PFS and OS rates compared with open surgery. Following the publication of these studies, the version 3.2019 of the NCCN guidelines recommended open surgery as the standard procedure for cervical cancer, while laparoscopic surgery is no longer recommended, which has caused a huge impact on the gynecology community.

Lymph node resection

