- **Pathologic evaluation:** Each patient must have a clear histologic diagnosis of cervical squamous cell carcinoma, cervical adenocarcinoma, or cervical adenosquamous carcinoma prior to radical cervical cancer surgery. If the cervical lesion is relatively evident, although the biopsy pathology shows patches of squamous cells without clear interstitial infiltration, the clinical presentation of the lesion is consistent with invasive cervical cancer, and then the patient may still be included in the study.
- **Clinical assessment:** cervical lesion size was measured by pelvic-enhanced MRI; the presence of metastases in the parametrium was determined by physical examination of the operator; and lymph node status was assessed by pelvic-enhanced MRI in combination with other imaging such as PET-CT.

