Supplementary therapy will be administered according to the postoperative pathological findings of the patients. Those with high-risk factors who have positive parametrium will be supplemented with external pelvic irradiation therapy + cisplatin/carboplatin concurrent chemotherapy, those with positive vaginal margins will be selected for external pelvic irradiation therapy + retrovaginal radiotherapy + cisplatin/carboplatin concurrent chemotherapy, and those with positive pelvic lymph nodes will be treated with 1 course of systemic chemotherapy + external pelvic irradiation radiotherapy ± extended field radiotherapy adjacent to the abdominal aorta + cisplatin concurrent chemotherapy + 3-6 courses of adjuvant systemic chemotherapy after radiotherapy. Those with intermediate risk factors will be treated with external pelvic irradiation radiotherapy + cisplatin concurrent chemotherapy, and those with positive proximal margins will be treated with external pelvic irradiation radiotherapy EBRT + cisplatin concurrent chemotherapy + retrovaginal radiotherapy. Targeted immunotherapeutic agents such as bevacizumab and PD-1, which have just obtained some results in clinical studies, are not considered in this trial for the time being. It could be used according doctor's orders.

3.10 Outcome measurements:

- 1) Main outcome indicators: 5-year OS.
- 2) Secondary outcome measurements: 5-year PFS, refer to RECIST criteria.
- 3) Other outcome measurements: operation time, anesthesia time, intraoperative bleeding volume, intraoperative complications, postoperative complications, postoperative pain score, postoperative hospital stay, one-month postoperative survival quality, one-year postoperative survival quality, sexual quality of life.
- 4) Other evaluation parameters: patient's demographic characteristics, signs and symptoms, stage, pathological type, tumor site, comorbidities, medical history, length of hospital stay and cost.
- 5) This study intends to sample and collect intraoperative tumor tissues from tumor patients and evaluate specific tumor stages with genetic testing to guide later treatments such as targeted or immune therapies. Histological studies and molecular studies will also be conducted.

	Pre-phase	0-12 months	12-24 months	24-36 months	36-60 months
Meet the researchers	X				
Obtain IRB approval	X				
Funding application	X				
Enrollment of study patients		X	X	X	
Data monitoring		X	X	X	X
Data collection		X	X	X	X
Data analysis					X

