5.3 Statistical methods

5.3.1 Outcome statistical methods

Statistical analysis of the study will be undertaken by the CTU of the Children's Hospital of Fudan University. Interventions began at the study design stage, based on key scientific questions, clear design protocols, and statistical analysis methods based on the properties of the primary outcome indicators, whereby sample sizes were calculated based on expected effects. After study inclusion begins until the last patient data collection is completed, a detailed SAP is written and uploaded to the Clinical Trials Registry website. The following is an overview of the statistical analysis strategy and methods.

All analyses will be performed on an intention-to-treat (ITT) basis, except for sensitivity

analysis that will be performed according to per-protocol (PP) treatment.

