5.3.2 Analysis of primary outcome data

a) This study is non-inferiority trial design, and the primary outcome is the rate of OS at 5 years. The hypothesis is as follows:

Hypothesis: Let π_1 denote the rate of OS at 5 years in the open surgery group, and let π_2 denote the rate of OS at 5 years in the minimally invasive surgery group, the non-inferiority margin =8%. The null hypothesis is $H_0: \pi_1 - \pi_2 \geq$ versus the alternative hypothesis is $H_1: \pi_1 - \pi_2 <$.

b) The curves of OS at 5 years will be estimated using the Kaplan-Meier method. The logrank test will be used to test the above hypothesis, the 5-year OS rate difference and its 95% confidence interval (CI) for the comparison between the two groups will be estimated. The minimally invasive surgery will be considered non-inferior to the open surgery if the one-sided 95% upper limit is less than , where = 8%, the predetermined non-inferiority margin.

c) Covariate adjusted analysis:

An analysis of the primary outcome adjusting for the blood loss during operation, operative duration, and postoperative pain score will be performed using Cox proportional hazards regression model. The hazard ratio of 5-year OS and 95% CI will be estimated.

d) Subgroup analysis:

We will stratify by tumour staging, and perform Cox proportional hazards regression model to estimate the hazard ratio and 95% CI of the 5-year OS.

e) Sensitivity analysis:

A sensitivity analysis of the primary outcome will be performed using the PP strategy.

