5.3.3 Secondary outcome analysis

a) The rate of PFS at 5 years:

Cox proportional hazards model will be used to estimate the hazard ratio and 95% CI for the effect of treatment on the 5-year PFS rate.

b) Analysis of continuous outcomes:

The continuous outcomes include operative duration, anesthesia time, blood loss during operation, postoperative pain score and postoperative hospital stay. The outcomes with normal distribution will be summarised using mean and standard deviation (SD), while the outcomes with non-normal distribution will be summarised using median and interquartile. The differences in the outcomes and 95% CIs will be analysed by generalised linear model (GLM) with treatment as fixed effect and with normal distribution and identity link function.

c) Analysis of binary outcomes:

The intraoperative complications, postoperative complications, one-month and one-year postoperative quality of life and sexual life will be treated as binary outcomes, and will

be summarised by number (%) of participants with the event. The differences in the outcomes and 95% CIs will be analysed by GLM with treatment as fixed effect and with binomial distribution and identity link function.

d) Interim analysis

The O'Brien Fleming method will be used to conduct an interim analysis three years after the study. If the study has conducted only once interim analysis, the α level will be set as 0.048 in the final analysis.

4. Safety analysis

Adverse events (AEs) will be summarised using the number of AEs, the number (%) of participants with AEs by groups.

5. All analyses will be performed with a two-sided significance level of 0.05 and conducted using SAS software, version 9.4 (SAS Institute).

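### The covariate-adjusted Cox analysis of overall survival conditions on blood loss, operative duration and pain, which are outcomes of the randomised surgery, so its hazard ratio is not the effect of assignment

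*Combined protocol and SAP*

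**What the plan says.** Section 5.3.2 c) of the combined protocol and SAP states: "An analysis of the primary outcome adjusting for the blood loss during operation, operative duration, and postoperative pain score will be performed". The model is a Cox regression reporting a hazard ratio for 5-year OS. No other covariate is named. Tumour stage appears only in the subgroup analysis in 5.3.2 d).

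The same three variables appear elsewhere as results of treatment:

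- Section 3.10 lists "operation time, anesthesia time, intraoperative bleeding volume, intraoperative complications, postoperative complications, postoperative pain score" among the outcome measurements.
- Section 5.3.3 b) states: "The continuous outcomes include operative duration, anesthesia time, blood loss during operation, postoperative pain score and postoperative hospital stay". It compares them between arms with treatment as the fixed effect.
- Section 2.2.2 (secondary objectives) includes a between-group comparison of surgical bleeding.

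The background in section 2.2.1 expects the arms to differ on them. Minimally invasive surgery "has unique advantages, such as less abdominal wall trauma, less pain, clearer vision and less bleeding", and the earlier small studies are summarised as showing that "laparoscopy was superior to open surgery in terms of operative time, intraoperative bleeding, and length of hospital stay".

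Section 5.3.1 adds: "All analyses will be performed on an intention-to-treat (ITT) basis", with a per-protocol sensitivity analysis as the exception. No section describes 5.3.2 c) as a mediation or direct-effect analysis.

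**The concern.** A covariate-adjusted treatment effect keeps its meaning when the covariates are fixed before randomisation. Here all three are produced by, or follow, the operation being compared. Conditioning on them has two consequences.

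1. Any effect of surgical approach on survival that acts through blood loss, duration or pain is removed from the hazard ratio.
2. If a covariate shares an unmeasured cause with survival (a technically difficult tumour, say), patients with equal blood loss in the two arms are no longer comparable on that cause. The hazard ratio is then biased even when surgery has no effect on survival.

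This is the only adjusted analysis of the primary outcome that the plan names, apart from the stage-stratified models. Readers will compare it with the main result, in a trial prompted by a disputed survival harm. An adjusted hazard ratio that departs from the effect of assignment could suggest harm or benefit where there is none, or hide a real difference. The model also contains no baseline prognostic factor, so it lacks the usual benefit of adjustment.

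**Working it through.** **The plan's own figures, and whether they depend on this analysis.** Section 3.12 gives 72% 5-year OS, an 8-point margin, one-sided alpha 0.025 and 80% power. Assuming no true difference:

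n per group = (1.960 + 0.842)² × 2 × 0.72 × 0.28 / 0.08² = 494.5, so 495.

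495 / 0.90 = 550 per group, or 1100 in total. Rounded up to a multiple of the block size of 6, this is 1104. The plan's figures reproduce and do not use the adjusted model. Nor does the decision rule in 5.3.2 b), which compares the 5-year OS difference with the margin.

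For scale, the margin (72% versus 64%) corresponds under proportional hazards to HR = ln 0.64 / ln 0.72 = 1.36.

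**When the adjustment would be harmless.** The adjusted hazard ratio stays close to the effect of assignment if surgery does not shift the covariates, or if they are unrelated to survival. Section 2.2.1 argues against the first condition. The documents do not address the second.

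**Bias with no true effect.** The inputs are assumptions, not figures from the documents:

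- g: log HR per SD of an unmeasured prognostic factor (tumour difficulty), 0.4 to 0.7
- r: within-arm correlation of that factor with the covariate, 0.3 to 0.5
- a: SDs by which minimally invasive surgery lowers the covariate, 0.5 to 1

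Once arm and covariate are held fixed, the expected value of the hidden factor differs between arms by r × a. The spurious log HR is therefore approximately g × r × a. This was compared with simulation: exponential survival calibrated to 72% at 5 years, censoring at 5 years, no dropout, one covariate, 400,000 patients per scenario. Trial-size results come from 1500 simulated trials of 1104.

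| Scenario | g × r × a | exp(g × r × a) | Simulated adjusted HR | SE of log HR | 95% CI excludes 1 |
|---|---|---|---|---|---|
| Low | 0.4 × 0.3 × 0.5 = 0.060 | 1.06 | 1.06 | 0.118 | about 7% |
| Middle | 0.55 × 0.4 × 0.75 = 0.165 | 1.18 | 1.17 | 0.122 | about 26% |
| High | 0.7 × 0.5 × 1 = 0.350 | 1.42 | 1.39 | 0.128 | about 73% |

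Unadjusted, the simulated HR was 0.99 to 1.01, the SE 0.114, and the interval excluded 1 in 5-6% of trials. The unadjusted SE agrees with 2/√(1104 × 0.28) = 0.114. The last column follows from the two before it. In the middle row, ln 1.17 / 0.122 = 1.29, which gives a two-sided rejection probability of about 25%.

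If surgery instead raised the covariate, the HRs would be the reciprocals: 0.94, 0.85 and 0.72. Section 2.2.1 does not point that way, so these are illustrative only.

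A separate simulation with g = 0.5 and r = 0.5 (300 trials of 1104 per scenario) moved a null HR from 0.99 to 1.12 for a shift of 0.5 SD, and from 1.00 to 1.26 for a shift of 1 SD. When surgery did not shift the covariate, or the covariate was unrelated to prognosis, both HRs were about 1.00.

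**Effect removed when the covariate is a mediator.** Again with assumed inputs, and with surgery lowering the covariate:

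| Direct HR | Shift (SD) | Log HR per SD | Unadjusted (total) HR | Adjusted HR |
|---|---|---|---|---|
| 1.35 | -0.5 | 0.2 | 1.20 | 1.34 |
| 1.35 | -1 | 0.3 | 0.99 | 1.34 |
| 1.00 | -0.75 | 0.2 | 0.87 | 1.01 |

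In the second row, arms with equal survival overall yield an adjusted HR close to the 1.36 that corresponds to the margin. In the third, a real benefit disappears.

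**The case against.** The strongest reply is about weight. Section 5.3.2 gives the adjusted model no success rule, no margin on the hazard-ratio scale and no tie-breaking role, and only 5.3.2 e) is called a sensitivity analysis. The primary conclusion is the same whatever this model shows. That stands, and it limits the severity.

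Second, the ITT statement in 5.3.1 is contrasted with per-protocol treatment, so it concerns who is analysed and in which arm. A Cox model on all randomised patients by assigned arm can satisfy it with any covariates. That also stands: the plan does not break its ITT promise. The fault is that the resulting hazard ratio is not the effect of assignment.

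Third, the size rests on assumed inputs, and at the low end it is almost nothing (7% against 5-6%). In the direction section 2.2.1 expects, with worse prognosis going with higher covariate values, the distortion runs against minimally invasive surgery. It is therefore conservative for a non-inferiority claim. This is fair, but a spurious signal of harm or a hidden benefit would still misinform readers.

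Fourth, 5.3.1 calls this an overview, with a detailed SAP to follow. That could excuse missing detail. It does not excuse naming covariates that should not be in the model.

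**Conclusion.** The concern holds. The plan treats the same three variables as effects of surgery and as quantities to hold constant when estimating the effect of surgery on survival, with no mediation aim stated. The adjusted hazard ratio therefore does not estimate the effect of assignment and cannot corroborate or contradict the main result.

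This conclusion follows from the plan's own text and needs no numerical assumption. The size does: under the assumed ranges a null effect becomes an adjusted HR of 1.06 to 1.39 in the expected direction, and the documents cannot narrow that range. The simulations used a single covariate, so they illustrate the problem and do not predict what this trial would show. The primary non-inferiority decision and the sample size of 1104 are untouched. This should be fixed, but it does not threaten the main conclusion.

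**What to change.** In section 5.3.2 c), remove blood loss, operative duration and postoperative pain score from the model. Replace them with prespecified factors recorded before randomisation. A reasonable set is stage (IB3 or IIA2), histology, age, tumour size and nodal status on preoperative imaging, and centre. The exact list is for the trial team to choose, provided that it is fixed in advance.

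Analyse the three removed variables only as outcomes, as 5.3.3 b) already does. If a model containing them is kept, label it an exploratory mediation analysis and state its assumptions, in particular no unmeasured common causes of the covariates and survival. It should also say how patients whose radical surgery is forgone intraoperatively are handled (sections 3.1 to 3.3 allow this). Their values may be missing or not comparable, and 5.3.4 gives no missing-data method.

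The cost is SAP wording only. The replacement covariates come from eligibility (section 2.2 of the research methods) and the preoperative assessment (3.7.1, where "cervical lesion size was measured by pelvic-enhanced MRI"), so no new data are needed. The detailed SAP that 5.3.1 promises is the natural place for the change.

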5.3.3 Secondary outcome analysis

a) The rate of PFS at 5 years:

Cox proportional hazards model will be used to estimate the hazard ratio and 95% CI for the effect of treatment on the 5-year PFS rate.

b) Analysis of continuous outcomes:

The continuous outcomes include operative duration, anesthesia time, blood loss during operation, postoperative pain score and postoperative hospital stay. The outcomes with normal distribution will be summarised using mean and standard deviation (SD), while the outcomes with non-normal distribution will be summarised using median and interquartile. The differences in the outcomes and 95% CIs will be analysed by generalised linear model (GLM) with treatment as fixed effect and with normal distribution and identity link function.

c) Analysis of binary outcomes:

The intraoperative complications, postoperative complications, one-month and one-year postoperative quality of life and sexual life will be treated as binary outcomes, and will

be summarised by number (%) of participants with the event. The differences in the outcomes and 95% CIs will be analysed by GLM with treatment as fixed effect and with binomial distribution and identity link function.

d) Interim analysis

The O'Brien Fleming method will be used to conduct an interim analysis three years after the study. If the study has conducted only once interim analysis, the α level will be set as 0.048 in the final analysis.

4. Safety analysis

Adverse events (AEs) will be summarised using the number of AEs, the number (%) of participants with AEs by groups.

5. All analyses will be performed with a two-sided significance level of 0.05 and conducted using SAS software, version 9.4 (SAS Institute).

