2.2.2 Secondary research objectives

To compare the 5-year progression free survival (PFS) of the two groups of patients with different surgical procedures.

To compare the relapse rate and relapse pattern between the two groups of patients with different surgical procedures.

To compare the functional status of each organ in the two groups.

To compare the effects of the two different surgical procedures on quality of life of the patients in the two groups.

To compare the difference in cost effectiveness between the two groups of patients.

To compare the amount of surgical bleeding, the incidence of surgery-related diseases, and intraoperative and postoperative complications between the two groups.

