3.7.3 Post-treatment follow-up records

One week after the end of treatment.

- a) Record postoperative pathology results and corresponding follow-up treatment plan
- b) Review laboratory tests (e.g. blood and urine routine test, coagulation function, blood liver, kidney function, electrolytes, drainage fluid creatinine)
- c) Postoperative indwelling catheter for 3-6 weeks and review of residual urine when the catheter is removed
- d) Postoperative complications (lymphatic cysts, dysuria, vaginal bleeding)

Review every 3 months for 2 years after completion of treatment with:

- a) Imaging examinations (chest CT + pelvic enhancement MRI + upper abdomen enhancement MRI or PET-CT)
- b) Tumor indicators: SCC antigen test (SCCA) and CA-125
- c) HPV and TCT test (once a year after completion of treatment)
- d) Adverse events recording
- e) Assessment of quality of survival and quality of sexual life using the Quality of Survival Scale for Cancer Patients (EORTC QLQ-C30 v3.0), the Cervical Cancer Sexual Life Scale (EORTC QLQ-CX24), and the Patient Reported Clinical Outcome Assessment Scale for Cervical Cancer PRO147 (V1.0).

After 2 years, the study will be reviewed every 6 months until the end of the trial. The review will include gynecological examination, tumor indicators (SCC antigen detection (SCCA) and CA-125), TCT examination and HPV examination, imaging (chest CT + pelvic enhancement MRI + upper abdomen enhancement MRI or PET-CT), and adverse event records.

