6.1 Patient-reported clinical outcome assessment scale PRO 147 (V1.0) for Cervical Cancer

The research team developed its own scale assessment related to patient reported outcomes in cervical cancer, which is based on the patient's perspective to assess the outcome after surgery. Cervical cancer is the fourth most common cancer in women, and its incidence has been on the rise in recent years, especially in younger patients. Since the uterus is located in the central pelvis, damage to pelvic floor tissues by surgery may cause a variety of complications such as urinary, intestinal, vaginal and lower limb dysfunction, which cannot be accurately assessed by conventional scales. Considering the high survival rate of patients with early-stage cervical cancer, it is especially important to study the short-term and long-term treatment effects for patients.

According to the U.S. Food and Drug Administration (FDA), patient reported outcome (PRO), a measure of any aspect of a patient's health status that comes directly from the patient, is a valid patient-centered, multifaceted means of evaluating treatment outcomes (such as symptom improvement or related function) that is widely used in clinical practice and trials.

The research team has developed the Patient-reported Clinical Outcome Assessment Scale PRO 147 (V 1.0) for cervical cancer based on this concept. This scale is based on three domains including daily life, psychological and social life, with 147 questions covering 13 latitudes: urinary dysfunction (URI), bowel dysfunction (BOW), pelvic organ prolapse (POP), loss of ovarian function (OVA), lymphatic dysfunction (LYM), neurological dysfunction (NEU), sexual dysfunction (SEX), anxiety (ANX) depression (DEP), stigma (SHA), life beliefs (BEL), social support (SUP), and daily life (LIF) to assess patient prognosis. At present, our scale has been screened, and completed the expert review, and now is in the pilot study phase. So far, there are about 100 patients have completed the survey, and the information is very useful for future complication management and surgical efficacy assessment.

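### Quality of life and sexual life come from multi-item scales but are to be analysed as yes/no outcomes, with no event, cut-off, scale or domain defined

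*Combined protocol and SAP*

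**What the plan says.** Comparing quality of life is a secondary objective in section 2.2.2: "To compare the effects of the two different surgical procedures on quality of life of the patients in the two groups". Section 3.10 (Outcome measurements) lists it one level lower, among the other outcomes: "one-month postoperative survival quality, one-year postoperative survival quality, sexual quality of life".

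The instruments are given in section 3.7.3, under the three-monthly reviews of the first two years: "Assessment of quality of survival and quality of sexual life using the Quality of Survival Scale for Cancer Patients", that is, the QLQ-C30, together with the QLQ-CX24 and PRO 147. Section 6.1 describes PRO 147 as a scale "with 147 questions covering 13 latitudes".

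For the analysis, section 5.3.3 c) groups these outcomes with intraoperative and postoperative complications: "one-month and one-year postoperative quality of life and sexual life will be treated as binary outcomes". They are to "be summarised by number (%) of participants with the event", and the arms are to be compared by a "GLM with treatment as fixed effect and with binomial distribution and identity link function". Section 5.3.3 b) keeps the postoperative pain score continuous, in a normal-distribution linear model with treatment as fixed effect.

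Section 5.3.1 calls all of this an overview. A detailed SAP is to be written between the start of inclusion and the end of data collection.

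**The concern.** A complication either happens or it does not. A scale score becomes an event only after someone chooses the scale, the domain, the time point and the threshold. The documents choose none of the scale, the domain or the threshold.

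Two things follow:

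- **The analysis cannot be carried out as written.** Different choices of scale and cut would give different percentages and possibly different conclusions. The choice is left to a period when outcome data are already accumulating.
- **Dichotomising a graded score usually discards information.** A real difference between the routes is then more likely to be reported as no difference. Section 2.5 calls quality of life an extremely important endpoint, so this is worth avoiding when the remedy is cheap.

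The plan is also uneven. In the same section the pain score stays continuous, and no reason is given for treating the quality-of-life scores differently.

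**Working it through.** **1. The plan's own figure.** Section 3.12 gives 5-year OS of 72%, a margin of 8%, one-sided alpha 0.025 and 80% power. Then n = (1.96 + 0.842)² × 2 × 0.72 × 0.28 / 0.08² = 494.5, so 495 per arm, which matches. Allowing for 10% drop-out, 495 / 0.90 = 550, raised to 552 per arm (1104 = 184 blocks of 6). No sample size is given for quality of life, so 495 is borrowed here as the number of completers.

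**2. Is an event defined?** The places where a definition could stand are:

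| Section | What it gives | Threshold or event |
|---|---|---|
| 3.7.3 | the three instruments | none |
| 3.10 | the outcome names | none |
| 5.3.3 c) | the summary and the model | none |
| 6.1, 6.2 | description of the scales | none |

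This finding needs no assumption.

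**3. Information kept after a cut.** Assume a normal score and a small shift between arms. With a share p on one side of the cut, efficiency relative to comparing means is φ(z_p)² / [p(1 − p)].

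- 50/50: 0.3989² / 0.25 = 0.637, a loss of 36%.
- 30/70: 0.576, a loss of 42%.
- 20/80: 0.2800² / 0.16 = 0.490, a loss of 51%.
- 10/90: 0.1755² / 0.09 = 0.342, a loss of 66%.

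In these terms, 495 per arm is worth about 315 at 50/50, 242 at 20/80 and 169 at 10/90.

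**4. Detectable difference** (two-sided 0.05, 80% power, 495 per arm).

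- Continuous score: (1.96 + 0.842) × √(2/495) = 0.178 SD.
- Median split: 0.178 / √0.637 = 0.223 SD.
- 20/80 split: 0.178 / √0.490 = 0.254 SD.

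If all 552 per arm completed, the figures would be 0.169, 0.211 and 0.241 SD. Fewer completers would raise all three in the same proportion. The increases of about 25% and 43% do not depend on n.

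**5. Power for an assumed shift of 0.2 SD** (495 per arm, two-sided 0.05).

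| Analysis | Proportions compared | Power | n per arm for 80% power |
|---|---|---|---|
| Continuous | – | 88.2% | 393 |
| 50/50 cut | 50% v 57.9% | 70.7% | 620 |
| 30/70 cut | 30% v 37.3% | 67.9% | 660 |
| 20/80 cut | 20% v 26.1% | 61.9% | 758 |
| 10/90 cut | 10% v 14.0% | 48.6% | 1049 |

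**6. Sensitivity to the normal assumption.** A simulated bounded score with 13 levels lost 35% when 41% of patients were at or above the cut, 47% when 75% were, 56% when 13% were and 63% when 87% were. For other shapes the general form is variance × f(cut)² / [p(1 − p)]:

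- A logistic score cut at the median loses 18%, and a uniform score 67%.
- A ceiling-type score, beta(5, 1.5), loses 42% at the median, 72% with 20% of patients below the cut and 12% with 70% below it.
- A few combinations lose nothing. For a t distribution with 4 degrees of freedom the median split has efficiency 1.12.

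**7. What the schedule supplies.** The preoperative list in section 3.7.1 (items a to m) contains no quality-of-life questionnaire. Section 3.7.3 has a visit one week after treatment, with no questionnaire listed, and then the three-monthly reviews that carry the scales. No listed visit supplies a one-month score. Section 3.7.3 counts reviews from the end of treatment, while section 7.3 counts them from surgery.

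**The case against.** The strongest reply is that section 5.3 is only an overview, so the event may yet be defined in the detailed SAP. A risk difference in responders is also a legitimate estimand once its threshold is fixed. Both points are fair. A reader might infer that no event will ever exist for these outcomes. The documents support only that none is given in them. The reply does not remove the point, because the binary treatment is stated as a decision that a later SAP would inherit. That SAP may be completed as late as the end of data collection, after discussion with the investigator team (section 5.2.1), whose surgeons know the allocation. Section 4.2.1 does keep statisticians unaware of the randomisation process, but section 4.1.3 has the principal investigator share in the analyses.

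Three stronger readings are tempting and should not be adopted:

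- **That a third to a half of the information is lost, as a fact about this trial.** That range fits a roughly normal score cut between 50/50 and about 20/80. The documents give no cut, SD or score distribution, and step 6 shows losses well outside the range.
- **That baseline adjustment would bring a further gain.** No preoperative questionnaire is scheduled, so there is currently no baseline score to adjust for.
- **That quality of life is a main argument for the minimally invasive route.** Sections 2.2.1 and 2.4 claim advantages such as less bleeding, less pain and shorter stay. Quality of life is something to compare, not a claimed advantage.

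It is also fair to say that the documents state no clinically important difference. They therefore cannot show that moving from 0.18 to 0.25 SD would change a conclusion. Nor does a continuous analysis by itself settle which of several scales and domains matters.

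**Conclusion.** The point holds in two parts of different strength.

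The first is unconditional. Section 5.3.3 c) commits scale-based outcomes to a yes/no analysis and the documents supply no event, cut-off, scale or domain. The planned percentages and risk differences cannot be produced from the plan, and the cut is open to choice while data accumulate.

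The second is conditional. For a roughly normal score the cut loses about 36% of the information at a median split, about 51% at 20/80 and more at extreme cuts. The detectable difference rises from 0.18 SD to 0.22 or 0.25 SD on the assumption of 495 completers per arm, which is probably generous since it is the OS sample size. Skewed, bounded or heavy-tailed scores can lose more or less than this.

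The primary OS comparison and its sample size are unaffected. This is a worthwhile correction to a secondary objective, not a threat to the trial's main conclusion.

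**What to change.** - Remove quality of life and sexual life from section 5.3.3 c) and keep the binomial model there for complications.
- Name the scale and domain that define each outcome, and the time points at which it is compared. With three instruments, and 13 dimensions in PRO 147 alone, say which comparison is the main one.
- Analyse the scores as continuous and report the mean difference with its 95% CI. Use either the linear model already in section 5.3.3 b) or a repeated-measures model over the scheduled post-treatment visits.
- If percentages of responders are wanted, make that analysis supplementary and fix the threshold now.
- Adjust for baseline only if a preoperative questionnaire is added to section 3.7.1.
- Reconcile the one-month outcome in sections 3.10 and 5.3.3 with section 3.7.3, and state whether visits are counted from surgery or from the end of treatment.

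The core change costs protocol and SAP wording and a little programming, with no new data. The trade-off is that results become mean differences, which some readers find less direct than percentages. A baseline or one-month questionnaire would cost more: it is an extra assessment, and a preoperative score cannot be recovered for patients already operated on.
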